### **3.1 Safety Information**

In 2008, the FDA issued an early communication about an ongoing safety review of TNF blockers and the development of lymphoma and other cancers in children and adolescents.

As of the December 2009 FDA Pediatric advisory committee, it was noted that in general, adverse events seen in studies submitted for the JIA indication were similar to those in the adult population, both in type and frequency.

Due to the relatively rare occurrence of these cancers, the limited number of pediatric patients treated with TNF blockers, and the possible role of other immunosuppressive therapies used concomitantly with TNF blockers, the FDA was unable at that time to fully characterize the strength of the association between using TNF blockers and developing a malignancy. Product labeling for all anti-TNF agents now includes language regarding the risk of pediatric malignancies as requested by the FDA.

Furthermore, in November 2011 the FDA requested that all manufacturers of TNF inhibitors undertake a coordinated effort to better understand the risks for malignancies that develop in patients who are 30 years of age and younger at the time of diagnosis. Reporting requirements for these events can be found in Section 7.1.8 Serious Adverse Event Reporting. A detailed discussion of the clinical toxicology, metabolism, pharmacology, and safety experience with adalimumab can be found in the current SmPC.

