### 6.1.1 Inclusion Criteria

The decision to prescribe either Humira or MTX must be made prior to the decision to enroll a patient in the registry. A patient will be eligible for participation if he/she meets the following criteria:

1. For a patient enrolling into the Humira arm; a pediatric patient diagnosed at any time with moderately to severely active polyarticular or polyarticular-course JIA (defined as arthritis affecting ≥ 5 joints at the time of diagnosis of polyarticular or polyarticular-course JIA) who has been prescribed Humira therapy according to the locally approved Humira product labeling and meets one of the following criteria:
  - a. Enrolled patients are 4 to 17 years of age as per approved Humira product label with the addition of polyarticular JIA patients 2 to < 4 years of age in countries with available local approval for this group of patients at the time of consent to the registry.
  - b. Newly initiated (within 24 months of registry entry) on Humira therapy and has received continuous (no more than 70 consecutive days off drug) Humira therapy, and the physician can provide available source documentation of SAEs, AEs of Special Interest, and dosing information since initiation of therapy;
  - c. Or is entering after participation (within 24 months of registry entry or, if longer, continuously treated at the same site) in an AbbVie Humira sponsored study, regardless of age or the number of joints with symptoms of polyarticular JIA, and has received continuous (no more than 70 consecutive days off drug) Humira therapy and the physician can provide available source documentation of SAEs, AEs of Special Interest, and dosing information since initiation of therapy.
2. For a patient enrolling into the MTX arm; a pediatric patient diagnosed at any time with moderately to severely active polyarticular or polyarticular-course JIA (defined as arthritis affecting ≥ 5 joints at the time of diagnosis of polyarticular or

polyarticular-course JIA) who is prescribed MTX therapy alone or in combination with other DMARDs according to the local product labeling (initiated treatment within 24 months of registry entry) and has received continuous therapy and the physician can provide available source documentation of SAEs, AEs of Special Interest, and dosing information since initiation of therapy.

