#### **6.5 Registry Duration**

The planned follow-up observation period is 10 years from enrollment into one of the treatment arms. The follow-up period for patients that switch from the MTX arm to the Humira arm will begin when they enroll into the Humira arm, in which case participation would be longer (i.e., up to 10 years from the time of the switch).

A patient may withdraw from the registry at any time without prejudice. If the physician decides it is in the best interest of the patient to discontinue Humira or MTX for any reason, treatment should be stopped. Physicians are encouraged to keep patients in the registry for a full 10-year observation period irrespective of future treatment decisions so important and complete safety and effectiveness information can be obtained. If the patient is not seen at a visit, efforts, i.e., phone, fax, letter, will be made to gather safety data through Year 10.

Patients in the MTX arm who are prescribed Humira treatment must be re-consented before enrolling in the Humira arm during the time that the enrollment period is open (i.e., until enrollment in the Humira treatment arm is complete).

If a patient withdraws or is withdrawn from the registry, this should be noted, along with the reason for withdrawal on the electronic study completion page. At the time of withdrawal from the registry, an assessment of the patient's current medical condition will be completed.

Patients who discontinue from the registry or transition to another HCP will be offered to participate in the direct to HCP follow-up process by their registry physician, as allowed

by applicable local regulations. If the patient (or Parent/Guardian for pediatric patients) agrees, a consent/assent and/or patient authorization for use/disclosure for data (as applicable) will be obtained.

Effectiveness measures will not be collected from patients participating in the direct to HCP process.

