In addition for patient's age  $\geq$  30 with a reported malignancy event, prior exposure to, or current use of antineoplastics, or other drugs which have a risk of malignancy as stated in their label and other relevant dosing information to estimate total exposure will be collected in the source documents and appropriate eCRF pages. At the time of the reported malignancy adverse event, sites will be asked if any of the prior and concomitant medications contributed to the event. Any medications used prior to the registry will be captured on the appropriate eCRF. Information on the reason for use, date(s) of administration including start and end dates, highest maintained dose, dosage information including dose, route and frequency, and reason for stopping the medication will be collected in the source documents and appropriate eCRF pages.

During registry participation, patients should not be enrolled into any interventional clinical trials.

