#### **7.1.8 Serious Adverse Event Reporting**

[figure not shown]
In the event of a SAE, and additionally, any nonserious event of malignancy in patients 30 years of age and younger, whether related to registry drug or not, the physician will notify the AbbVie Clinical Pharmacovigilance Team within 24 hours of the physician becoming aware of the event by entering the Serious Adverse Event or nonserious event of malignancy in patients 30 years of age and younger into the electronic data capture (EDC) system. Serious Adverse Events and nonserious events of malignancy in patients 30 years of age and younger, that occur prior to the site having access to the EDC system or if the EDC is not operable should be documented on the SAE Non-CRF paper forms and emailed to AbbVie Clinical Pharmacovigilance or faxed to AbbVie Clinical Pharmacovigilance within 24 hours of being made aware of the Serious Adverse Event.

For SAE concerns, contact the Immunology Safety Team at:

For any subject safety concerns, please contact the Primary Study Designated Physician listed below:

Should in case of subject safety concerns or medical emergencies the Primary Study Designated Physician be unavailable, please call the following central back-up number:

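### Section 6.6.4 asks for the targeted malignancy drug history at age 30 or older, while Sections 3.1 and 7.1.8 use 30 and younger, so the request would rarely apply in this registry

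*Supplement*

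**What the plan says.** Protocol Section 6.6.4 (Prior and Concomitant Medications) has a paragraph on malignancy cases that opens with "In addition for patient's age $\geq$ 30 with a reported malignancy event". For that group it requests "prior exposure to, or current use of antineoplastics, or other drugs which have a risk of malignancy as stated in their label", together with dosing detail sufficient to estimate total exposure. Later sentences in the paragraph ask sites whether any prior or concomitant drug contributed to the malignancy. They also say that medications used before the registry will be captured with dates, dose and reason for stopping. These later sentences repeat no age limit.

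Two other sections use an age of 30 for malignancy, both in the opposite direction. Section 3.1 reports a regulator's request to manufacturers of TNF inhibitors about "malignancies that develop in patients who are 30 years of age and younger at the time of diagnosis" and refers to Section 7.1.8 for reporting. Section 7.1.8 requires 24-hour notification of SAEs and also of "any nonserious event of malignancy in patients 30 years of age and younger, whether related to registry drug or not".

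On who can be in the registry, Section 6.1.1 says "Enrolled patients are 4 to 17 years of age as per approved Humira product label", with children aged 2 to under 4 added where locally approved. Patients coming from a sponsor study may enter "regardless of age or the number of joints with symptoms of polyarticular JIA". Section 6.5 says "The planned follow-up observation period is 10 years from enrollment into one of the treatment arms", and the clock restarts when a patient moves from the MTX arm to the Humira arm.

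**The concern.** The only origin the protocol gives for a 30-year limit is the regulator's interest in younger patients. No section gives a reason for asking more about patients aged 30 or older, and a paediatric registry with 10 years of follow-up has few of them. The likeliest explanation is a reversed inequality.

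The stakes lie in how malignancy cases can be interpreted. Section 10.6 gives the low frequency of malignancies, with heart failure, as the reason for the second five years of follow-up. Section 3.1 says the link between TNF blockers and malignancy could not be fully characterised, partly because of other immunosuppressive drugs given alongside them. With few cases expected, the drug history of each one carries weight, and old histories become harder to recover with time.

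**Working it through.** The protocol states no figure to reproduce here. The check has three parts.

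**1. The age limits side by side**

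| Section | Purpose | Age group |
|---|---|---|
| 3.1 | Regulator's request | 30 or younger at diagnosis |
| 7.1.8 | 24-hour notification of nonserious malignancy | 30 or younger |
| 6.6.4 | Targeted drug history after a malignancy | 30 or older |

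The only shared age is 30. Section 6.6.4 also does not say at what date age is taken.

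**2. Who can reach 30**

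Inputs: upper entry age 17, that is under 18 (Section 6.1.1); follow-up of 10 years (Section 6.5); planned enrolment window of three years (Section 10.6), which limits how late a switch can occur. The MTX criterion says only that the patient is paediatric; I take the same upper age, as in the title of Figure 1.

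Formula: oldest attainable age = upper entry age + wait before a switch + 10.

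- Newly enrolled, no switch: under 18 + 0 + 10 = under 28. None reaches 30.
- MTX-to-Humira switcher, age limit not reapplied: under 18 + 3 + 10 = under 31. A wait of two years gives under 30, so the wait must exceed two years.
- MTX-to-Humira switcher, age limit reapplied: under 28. Inclusion criterion 3 requires switchers to meet the inclusion criteria, which favours this reading.
- Roll-over patient: no age limit, but reaching 30 within 10 years needs entry at 30 − 10 = 20 or older.

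For roll-overs, years of follow-up at 30 or older = entry age − 20: 2 of 10 years for entry at 22, 4 of 10 at 24, 6 of 10 at 26.

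The documents give no age distribution, so a share of follow-up needs assumptions. Suppose adult roll-overs enter at ages uniform on 18 to 24, everyone else enters under 18 without a late switch, and all complete 10 years. Mean time at 30 or older per adult roll-over = (1/6) × (4²/2) = 1.33 years, or 13.3% of 10 years. Multiply by the adult roll-over share of the cohort:

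| Adult roll-overs in cohort | Follow-up at age 30 or older |
|---|---|
| 0% | 0% |
| 5% | 0.7% |
| 10% | 1.3% |
| 15% | 2.0% |
| 25% | 3.3% |

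As a ceiling on the share, Section 3.0 counts 228 patients in DE038, M10-240 and M10-444 together, and 228/800 = 28.5%. The true adult share must be lower: roll-over is offered only from DE038 and M10-444 (Section 6.1), and one of the two sponsor studies described in Section 3.0 enrolled very young or very light children.

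**3. What is recorded anyway**

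- At every age, Section 6.6.4 records prior DMARDs and biologics (highest maintained dose, duration, last date, reason for stopping). It also records every medication taken at screening or during the registry, with dates, dose, route and frequency.
- Section 6.6.2 asks for retrospective MTX and Humira exposure from first dose.
- Table 1 lists previous and concomitant JIA therapies, and concomitant medications at the time of an SAE or event of special interest. It has no row for prior antineoplastics given for other reasons.
- In the direct-to-HCP process, Sections 6.7.2 and 7.3 limit routine medication data to polyarticular JIA drugs and Humira/MTX dates, although malignancies are collected there through Year 10.

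If the age limit governs the whole paragraph, a younger patient with a malignancy loses the targeted history of prior antineoplastics outside the DMARD class and of other drugs with a labelled malignancy risk, with total-exposure dosing. If it governs only the first sentence, the loss is smaller.

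**The case against.** The best counter-argument is that little is lost. The immunosuppressants that concern Section 3.1 are mostly DMARDs, biologics or drugs taken during the registry, and these are recorded for everyone. The later sentences of the same paragraph may already apply to all ages. Malignancies themselves are collected at every age through Year 10, and expedited reporting under Section 7.1.8 uses the younger group. Most of this stands, and it limits the severity. It does not remove the point: if general recording covered everything, the paragraph would serve no purpose, and in the direct-to-HCP process general recording is narrow.

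A second objection is that the point rests on one machine-read sign. Elsewhere the extraction seems to drop comparison signs: the joint-count definition has one in Section 6.1.1 and none in Section 6.3. Those look like omissions, not reversals, and here a sign is present. But Appendix I does not itemise this sentence, so there is no second copy to compare. The sign must be checked on the page.

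A reader might also infer that the plan fails the regulator's request. The documents do not support that. Section 3.1 describes a wish to understand risk in younger patients and does not list this drug history as a requirement. The link to Section 6.6.4 is an inference from the shared limit and subject.

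**Conclusion.** Section 6.6.4 is wrong as written, with moderate severity. Its age limit conflicts with Sections 3.1 and 7.1.8, and it excludes every newly enrolled patient throughout follow-up. It could apply only to older roll-overs and perhaps a few late switchers: about 0% to 3.3% of follow-up time under the stated assumptions on the share and entry ages of adult roll-overs.

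That range describes how often patients are old enough for the request to apply. A reader might take it to mean that almost no malignancy case would have drug-exposure data, against almost all once the sign is turned. The documents do not support this, because the general medication rules apply at all ages. The loss is mainly the targeted history described above, and it is larger for patients in the direct-to-HCP process. The safety rates in Section 10.3 and the sample size in Section 10.6 are unaffected. The conclusion assumes that the printed sign matches the extracted text.

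**What to change.** 1. Check the sign against the page of the sponsor's PDF.
2. If it is as extracted, reconcile Section 6.6.4 with Sections 3.1 and 7.1.8, using either 30 and younger or all patients with a malignancy. The second is simpler and also keeps roll-over patients who pass 30 during follow-up. If an age limit stays, state that it means age at diagnosis.
3. State whether the later sentences of the paragraph, on medications before the registry and on contributing drugs, apply to all patients, and whether the request covers malignancies reported through the direct-to-HCP process.
4. Check which age condition the eCRF uses, and correct it if it follows the printed text.
5. Query the drug history for malignancies already reported in patients whom the printed rule left out.

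The cost is one symbol and a sentence or two in the next amendment, an eCRF check and a small number of site queries. Treatment, visits and analyses do not change.

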#### **6.6.5 Safety Data Collection**

The following safety information will be collected from the time the parental consent and patient assent forms are signed: AEs of Special Interest and SAEs. The Physician will assess and record the AE in detail including the date of onset, description, severity, time course, duration and outcome, relationship of the AE to treatment, an event diagnosis, if known, and any action(s) taken. For SAEs considered "possibly related," "probably not related" and "not related" to the registry treatment, the Physician will provide the alternative etiology of the event. Information about medications taken to treat the SAE or the Adverse Event of Special Interest will be collected.

During the first 5 years of the registry, all available patient data, including SAEs, AESI as defined by the protocol and pregnancies will be collected at each doctor's visit. However, SAEs, AESI and pregnancy information can be collected at any time during the registry, not only at each doctor's visit. During Years 6 through 10 of the registry, patient data will be collected annually, including SAEs, a subset of AESI that includes congestive heart failure, malignancies, AEs at least possibly related to and/or leading to discontinuation of registry treatment, and pregnancies (Figure 1). Polyarticular JIA patients 2 to < 4 years of age, in countries with available local approval for this group of patients at the time of consent to the registry, will have SAEs, AESI, and pregnancy (potentially at the age when patient can become pregnant) collected for the full 10 years as defined by the protocol (Figure 2). Patients who develop an SAE or Adverse Events of Special Interest (AESI) while in the registry will be followed throughout the patient's participation in the registry until satisfactory conclusion or until 70 days following the last registry dose (whichever is longer).

For patients participating in the HCP process, safety data will be collected by the participating HCP using the HCP questionnaire on an annual basis. The questionnaire to be used through Year 5 focuses on the collection of Adverse Events of Special Interest (AESI), hospitalizations, surgeries, and death. The questionnaire to be used for Years 6 through 10 focuses on collection of a subset of AESI that includes congestive heart failure and malignancies, hospitalizations, surgeries, and death (Figure 1). Polyarticular JIA patients 2 to < 4 years of age in countries with available local approval for this group, will have AESI, hospitalizations, surgeries and death collected for the full 10 years as defined by the protocol (Figure 2). The questionnaire may be completed by the registry physician or the patient's current HCP (if the patient is no longer under the care of a registry physician).

All patients who participate in or discontinue from the registry during the first 5 years will be followed for SAEs and AEs of Special Interest until satisfactory conclusion or for 70 days after their last dose of registry drug (whichever is longer) to further evaluate safety. All patients who participate in or discontinue from the registry during Years 6

through 10, will be followed for all SAEs, CHF and malignancies until satisfactory conclusion or for 70 days after last dose of registry drug (whichever is longer) to evaluate safety. All patients who participate in or discontinue from the direct to HCP follow-up process up through Year 5 will be followed for AESI, hospitalizations, surgeries and death until satisfactory conclusion or for 70 days after their last dose of registry drug (whichever is longer) to further evaluate safety. All patients who participate in or discontinue from the direct to HCP follow-up process up during Registry Year 6 through Year 10 will be followed for malignancies, CHF, hospitalizations, surgeries, and death until satisfactory conclusion or for 70 days after their last dose of registry drug (whichever is longer) to further evaluate safety ([Figure 1](#)).

All polyarticular JIA patients 2 to < 4 years of age in countries with available local approval for this group of patients at the time of consent to the registry who participate in or discontinue from the Registry up through Year 10 will be followed for AESI and SAEs until satisfactory conclusion or for 70 days after their last dose of registry drug (whichever is longer) to further evaluate safety. All polyarticular JIA patients 2 to < 4 years of age who participate in or discontinue from the direct to HCP follow-up process up through Registry Year 10 will be followed for AESI, hospitalizations, surgeries and death until satisfactory conclusion or for 70 days after their last dose of registry drug (whichever is longer) to further evaluate safety ([Figure 2](#)).

Follow-up contact can include a certified letter or phone call to the patient. All contact must be clearly documented in the patient's registry file.

All medications used to treat these events will also be captured. A complete list of the Adverse Events of Special Interest can be found in Section [7.1.3](#).

#### **6.6.6 Physician Global Assessment and Patient Reported Outcome Measurements**

Information about the effectiveness of Humira or MTX therapy will be provided by the patient's parent or guardian and their physician. Patients and/or parents will complete the questions directly on the paper case report form (CRF) and the CRF pages will be

considered source documents. Effectiveness of therapy provided by the patient will be collected with clinical assessments beginning with the enrollment visit, at regularly scheduled visits which are closest to Months 1 and 3 (if applicable) and 6 and then every 6 months through Year 5. The following clinical assessments will be used: physical function of the Disability Index of Childhood Health Assessment Questionnaire (DICHAQ), and Parent's Global Assessment of Patient's Disease Activity (VAS) and Parent's Assessment of patient's pain (VAS). Effectiveness of therapy provided by the physician will be collected through the Physician's Global Assessment of Disease Activity (VAS).

The Child Health Questionnaire (CHQ-PF50) in [Appendix G](#) will be used to assess quality of life for children with polyarticular JIA through Year 5.

Physician Global Assessment and Patient Reported Outcome Measurements will not be collected after the completion of Year 5.

#### **6.6.7 Joint Assessment**

A thirty-nine joint assessment ([Appendix D](#)) will be recorded starting at the enrollment visit and at each registry visit thereafter through Year 5 to assess the number of active joints.

